6. BENEFITS

We believe that all participants will benefit by learning (from the study questionnaires and measurements) about their health and physical activity levels. Those who successfully improve their physical activity levels will have achieved desired goals. Over the study period all participants will benefit from receiving health information.

We believe society will benefit from the results of this project in that it will inform further research aimed at developing effective and appropriate physical activity programs for low-income populations in this age group.

It will shed light on how best to deliver physical activity advice to enhance adoption and maintenance of regular physical activity through programs that include individual-level behavioral skill-building and identification of neighborhood assets for and barriers to regular physical activity. The delivery of these programs in community settings such as congregate housing sites by trained lay advisors and facilitators can substantially broaden the reach of the physical activity interventions to underserved populations at potentially lower-cost than traditional face-to-face or health care provider-delivered approaches. These are public health issues of immense proportions, particularly with the continued growth of the older segment of the U.S. population and the substantial prevalence of inactivity among that population group in general and lower-income segments in particular. In summary, we believe the risks can be kept very low whereas the benefits to participants and society are quite substantial.

7. PRIVACY AND CONFIDENTIALITY

All participant information and specimens are handled in compliance with the Health Insurance Portability and Accountability Act (HIPAA) and privacy policies of Stanford University, Stanford Health Care, and Stanford Children's Health.

Citizen Science to Promote Sustained Physical Activity in Low-Income Communities

NCT03041415

5/5/2022

[name], Principal Investigator
Stanford University
[name]

Steps for Change Statistical Analysis Plan

Sample size calculation and data analysis plan

Sample size estimates have been developed to test the study's primary question evaluating the potential superiority of the ALED+Our Voice intervention in increasing 12-month weekly walking minutes relative to those achieved in the ALED+health education comparison intervention. Using a two-tailed 95% confidence interval on the effect size (Cohen's d), we will evaluate how the estimated true effect size compares with a critical effect size magnitude, set a priori, reflecting the threshold of clinical significance between the two interventions.

The effect size (Cohen's d) is the standardized difference between the rates of change in total walking minutes/week over the 12-month period. The critical effect size value is based on a clinically meaningful difference between arms of 30 min of total walking per week and a within-arm standard deviation of 90. In enrolling at least 140 subjects per study arm, our final total sample size of 300 will provide greater than 80% power to determine 12-month superiority between the two study arms. Because standard imputation methods will be used for missing data in this intent-to-treat trial, all enrolled participants will in actuality contribute to the study analyses.

Analysis of the primary outcome and secondary outcomes of interest

The data will be analyzed using mixed-effects linear regression models. Mixed-effects linear regression effectively addresses both missing data and early dropout in "intent-to-treat" analysis. Change in 12-month weekly walking minutes is the primary outcome, with centered arm assignment as the independent variable, and the centered baseline value, community housing site, and sex as covariates. To account for the cluster randomization design, community housing site will be included as a random intercept term. Multiple imputations will be performed by replacing missing 12-month values with a set of plausible values using the option of imputation by fully conditional specification methods (ten imputations will be done). Imputation results will then be combined. All reported out-comes will use intent-to-treat (ITT) principles. The 12-month time point was chosen for the primary analysis given that 12 months provides sufficient time for the multi-level intervention to have impacts on local environmental and policy outcomes in addition to person-level out-comes; provides enough time to evaluate program maintenance effects; and controls for seasonal effects given that it occurs during the same time of the year as baseline measurement.

Similar mixed-effects linear regression techniques will be used to address the secondary outcomes of interest, e.g., intervention impacts on additional physical activity variables, clinical measures, physical function, and rated well-being variables, as well as impacts of the interventions at the other assessment time points (6, 18, and 24 months).

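### Does the SAP leave open whether the 95% CI must exclude zero or the clinical threshold before superiority is claimed?

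*SAP*

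**What the plan says.** Under *Sample size calculation and data analysis plan*, the SAP says the sample size was developed to "test the study's primary question evaluating the potential superiority of the ALED+Our Voice intervention in increasing 12-month weekly walking minutes" relative to the comparison arm. It then describes a two-sided 95% interval on Cohen's d and says "we will evaluate how the estimated true effect size compares with a critical effect size magnitude, set a priori", with that magnitude "reflecting the threshold of clinical significance between the two interventions". The critical value rests on "a clinically meaningful difference between arms of 30 min of total walking per week and a within-arm standard deviation of 90". The SAP does not print the ratio, but it is 30/90 = 0.333. Cohen's d itself "is the standardized difference between the rates of change in total walking minutes/week over the 12-month period"; the SD used to standardise the estimate is not named. With at least 140 per arm, the total of 300 "will provide greater than 80% power to determine 12-month superiority between the two study arms".

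Under *Analysis of the primary outcome and secondary outcomes of interest*, the SAP gives the model: "Change in 12-month weekly walking minutes is the primary outcome, with centered arm assignment as the independent variable". Baseline value, site and sex are covariates, site enters as a random intercept, and results are combined over ten imputations. This section names no null value and does not mention d. The protocol has no statistical section that adds to this.

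**The concern.** The only comparison written down for the interval is with the clinical threshold; zero is not mentioned. A literal reader could conclude that superiority requires the whole interval to lie above 0.333. The power statement cannot belong to that rule, so the text appears to state one criterion and to power another.

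If the choice were truly open, a result between the two cut-offs could be called a success or a failure after the data were seen. The unnamed SD adds a smaller uncertainty. With the planning SD of 90, d = 0.333 and 30 min/week are the same threshold. With an observed SD, the threshold in minutes becomes SD/3.

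**Working it through.** **Inputs.** From the SAP's sample size section: difference 30 min/week, within-arm SD 90, two-sided 95% interval, total 300 with at least 140 per arm. Assumed: 1:1 allocation (150 per arm), normal approximation, no clustering and no gain from baseline adjustment.

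**1. Reproduce the plan's power, testing against 0.**

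SE(d) = √(2/n). At 150 per arm, SE = √(2/150) = 0.1155.

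Power = Φ(0.333/0.1155 − 1.96) = Φ(2.887 − 1.96) = 82.3% (noncentral t: 82.1%).

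At 140 per arm, SE = 0.1195 and power = Φ(2.789 − 1.96) = 79.6%.

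The statement of more than 80% is therefore reproduced at the total of 300 to which the SAP attaches it, and just missed at the 140 minimum.

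**2. Try the rival rules at the same true effect.**

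- Lower limit above 0.333: Φ((0.333 − 0.333)/SE − 1.96) = Φ(−1.96) = 2.5%. This holds at any sample size, because the assumed truth sits on the boundary.
- Point estimate at or above 0.333: 50%, by symmetry, again at any sample size.

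Neither comes near 80%. For 80% power to clear 0.333 at 150 per arm, the true d would have to be 0.333 + (1.960 + 0.842) × 0.1155 = 0.657, or 0.657 × 90 ≈ 59 min/week. That is about twice the planning difference, and the SAP assumes no such effect.

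**3. Where the two interval rules would disagree.**

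Half-width = 1.96 × 0.1155 × 90 = 20.4 min. Zero is excluded when the observed difference is above 20.4 min. The threshold is cleared only above 30 + 20.4 = 50.4 min.

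With a standard error of 0.1155 × 90 = 10.4 min, the probability that the observed difference falls between these cut-offs depends on the true difference (values other than 30 are assumed):

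| True difference (min/week) | P(rules disagree) |
|---|---|
| 0 | 2.5% |
| 10 | 16% |
| 20 | 48% |
| 30 | 80% |
| 40 | 81% |
| 50 | 51% |
| 60 | 18% |

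**4. The unnamed SD.** If the observed SD standardises d, the threshold of 0.333 equals 70/3 = 23.3 min at SD 70, 90/3 = 30 min at SD 90 and 120/3 = 40 min at SD 120 (70 and 120 are assumed). Dividing by a positive SD does not change the sign of the estimate or move zero, so this choice has no bearing on whether 0 is excluded.

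**The case for a change.** The strongest case for a change is that the SAP gives the comparison with the critical value as its way of answering the primary question and states no separate test. Someone applying that sentence alone could call an observed 35 min/week a failure, whereas a test against 0 would call it a success. If the truth is the planned 30 min, about 80% of trials would fall in the range where the rules differ. A rule left unwritten could also be chosen late, and one sentence would settle it at no cost.

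It is true that no sentence names the value to be excluded, and the arithmetic is right. The rest is weaker. The rival rule contradicts the power claim in the same section, so it is not an equal competitor. The cited sentence promises to evaluate how an estimate compares with a threshold of clinical significance; it does not say that superiority fails unless the threshold is cleared. The 80% figure applies to true differences of about 30 to 45 min and falls away on either side, and it counts disagreement with a reading that the plan's own figures rule out. The SD point concerns only the clinical gloss, and the SAP supplies 90 as the basis of the critical value. Reading that threshold in minutes rather than as d would be a matter of preference.

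**Conclusion.** No change is needed. The missing rule is a gap that analysts fill sensibly: superiority is judged by whether the two-sided 95% interval for the pooled arm coefficient excludes 0 in favour of ALED plus Our Voice, and the critical effect size is then used to judge clinical importance. Of the three rules checked, only this one agrees with the stated power (82.3% at 150 per arm, against 2.5% and 50%). Writing it down would record what the plan already implies, without altering the analysis, the sample size or the conclusion.

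The figures assume SD 90, equal arms and no clustering. The protocol's *Procedures* section (2a) and the SAP both have randomisation by housing site, and the SAP gives no intracluster correlation. By the normal approximation, 80% power needs 2 × (90/30)² × (1.960 + 0.842)² ≈ 141 per arm, so a design effect above about 150/141 = 1.06 would bring power against 0 below 80%. That is a separate matter from which value the interval must exclude. Clustering widens the interval under either rule and does not make the threshold the more likely null.

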2. STUDY PROCEDURES

a. Procedures

Recruitment

Subjects will be recruited from affordable housing serving mid-life and older adults from the San Francisco Bay Area.

The primary recruitment methods will consist of targeted mailings to residents of each housing site or low income older adults living near these affordable housing sites. We will supplement these approaches with outreach communications tailored to each housing site (e.g., flyers posted in housing site common areas).

Eligibility Screen

Individuals will go through an initial telephone, face-to-face or online screening process. Those who are initially eligible will proceed to an information session where the study activities and procedures will be explained in greater detail. If interested in continuing at that point, individuals will read and sign an informed consent form approved by Stanford University IRB.

Those adults meeting study criteria in relation to age, physical activity and general health status, and interest will be invited to participate in a baseline assessment. Demographic, health/medical, perceived environment, and psychosocial and behavioral information will be collected from study participants by interview or self-administered questionnaire.

Study Assessments

Study assessments will be collected at baseline, 6, 12, 18, and 24 months for all study participants. Physiologic measures will include ambulatory activity monitors that measure movement throughout the day in the person's natural environment, and physical measurements (height, weight, resting blood pressure, physical function field tests) collected from study participants by trained study staff. These data and material will be obtained specifically for research purposes.

Persons completing this assessment who are eligible will be enrolled in the study.

Study Interventions

Study interventions consists of housing site-based randomization to one of the two study arms: (1) the Active Living Every Day (ALED) program plus a Health

education program, or (2) ALED plus Our Voice neighborhood engagement program. The intervention period for each study arm lasts for at least 12 months and up to 24 months.

b. Procedure Risks

The research procedures are not invasive and pose minimal risk to study participants.

c. Use of Deception in the Study

NA

d. Use of Audio and Video Recordings

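### The SAP's power figure for N = 300 is that of an individually randomised trial; nothing in the documents supports it for the site-randomised design

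*SAP*

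**What the plan says.** The sample-size text (SAP, sample size calculation and data analysis plan) builds its critical effect size on "a clinically meaningful difference between arms of 30 min of total walking per week and a within-arm standard deviation of 90". It sets a minimum of 140 participants per arm, and concludes that "our final total sample size of 300 will provide greater than 80% power to determine 12-month superiority between the two study arms". It counts every enrolled participant, because missing values will be imputed. That text does not mention clustering.

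The Protocol describes the allocation as follows (section 2a, Study Interventions): "Study interventions consists of housing site-based randomization to one of the two study arms". The SAP's section on the primary analysis agrees: "To account for the cluster randomization design, community housing site will be included as a random intercept term". The same section describes the primary model "with centered arm assignment as the independent variable, and the centered baseline value, community housing site, and sex as covariates".

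Neither document gives an ICC, a number of sites, a site size or a design effect. The sample-size text also does not say whether the SD of 90 is before or after adjustment for baseline.

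**The concern.** When whole sites are randomised, participants at one site tend to resemble each other. The variance of the arm difference is then multiplied by a design effect of 1 + (m − 1) × ICC, where m is the site size. The number of sites also limits the degrees of freedom for the arm comparison. A power figure that leaves out both belongs to a different design.

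This sentence is the only justification given for N = 300. If the 12-month result is null or imprecise, readers will judge it against the stated power, and the SAP does not let them tell whether that power applies to the trial as randomised.

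**Working it through.** **Inputs from the documents.** Difference 30 min/week and SD 90, so d = 30/90 = 0.333. Two-sided 0.05, from the two-tailed 95% interval. N = 300 in total, at least 140 per arm. The allocation ratio is not stated, so 150/150 is taken as the base case and 140/160 as the extreme that the minimum allows.

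**The null.** The SAP does not state one; it says "we will evaluate how the estimated true effect size compares with a critical effect size magnitude, set a priori". Zero is the reading that reproduces the stated power. If success instead required a 95% interval wholly above 30 min, its probability at a true difference of 30 min would be 2.5%. Zero is used below, as an inference.

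**Step 1: reproduce the SAP's figure.** Noncentral t, independent participants, ncp = d / √(1/n₁ + 1/n₂).

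- 150/150: 0.333 × √75 = 2.887, df 298, power 82.1%.
- 140/160: ncp 2.880, df 298, power 81.9%.
- 140/140: 0.333 × √70 = 2.789, df 278, power 79.4%.

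The claim for 300 reproduces, with about two points to spare. The stated minimum in both arms falls just short of 80% even without clustering.

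**Step 2: how much clustering the margin absorbs.** With clustering, ncp = 0.333 × √(75/DEFF). Keeping df at 298 and treating 90 as the SD in the analysis, power reaches 80% at DEFF = 1.0549. Then ICC = 0.0549/(m − 1). The site counts are assumed, with equal sizes:

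- 10 sites, m = 30: 0.0549/29 = 0.0019
- 20 sites, m = 15: 0.0549/14 = 0.0039
- 30 sites, m = 10: 0.0549/9 = 0.0061

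**Step 3: degrees of freedom.** With a t reference on sites − 2 df, power at ICC 0 is 71.6% (8 df), 77.9% (18 df) and 79.6% (28 df).

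**Step 4: baseline adjustment.** Suppose 90 is the SD before adjustment and baseline correlates r with the change. Then ncp is multiplied by 1/√(1 − r²), with the ICC assumed unchanged. The table shows power (%) as individual df / sites − 2 df. ICCs, site counts and r are all assumed, so this is a set of scenarios and not a likely range.

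| Sites | SD 90 is | ICC 0.005 | 0.01 | 0.02 | 0.05 |
|---|---|---|---|---|---|
| 10 | analysis SD | 76.7/65.8 | 71.7/60.7 | 62.9/52.3 | 45.2/36.9 |
| 20 | analysis SD | 79.4/75.2 | 76.9/72.5 | 72.0/67.5 | 59.8/55.4 |
| 30 | analysis SD | 80.4/77.8 | 78.7/76.1 | 75.5/72.8 | 66.6/63.9 |
| 10 | unadjusted, r = 0.5 | 87.4/77.9 | 83.3/73.0 | 75.3/64.3 | 56.5/46.6 |
| 20 | unadjusted, r = 0.5 | 89.5/86.1 | 87.5/83.9 | 83.6/79.6 | 72.2/67.7 |
| 30 | unadjusted, r = 0.5 | 90.2/88.2 | 88.9/86.9 | 86.4/84.2 | 78.8/76.2 |

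With 90 as the analysis SD, one of 24 values is above 80%. With 90 unadjusted and r = 0.5, 13 of 24 are. At r = 0.3 the room is smaller: the largest ICC that keeps 80% on individual df is 0.0055, 0.0114 or 0.0177 for 10, 20 or 30 sites. On sites − 2 df it is none, 0.0031 or 0.0097.

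**The case against.** **Baseline adjustment may compensate.** This is the strongest reply, and part of it stands. The model adjusts for baseline, and the r = 0.5 rows show power above 82.1% in many scenarios. But the SAP states no correlation, claims no such gain and leaves the meaning of its SD open. The reply shows that the figure could be right; it does not supply the missing support.

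**The random intercept already deals with clustering.** It is there so that the arm comparison reflects the site randomisation. It does not give back precision lost to clustering, and it puts nothing into the power calculation.

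**The Protocol allows up to 432 participants.** Section 4a ties that ceiling to no power or clustering calculation, and the SAP's claim is made at 300.

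**The ICCs are assumed.** They are, because the documents give none. The conclusion needs no particular value: the sentence has no allowance for clustering, and its margin is a design effect of about 1.055.

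**The practical effect is limited.** This is fair. Recalculating power changes neither the estimate nor its confidence interval. It corrects the statement on which the sample size rests.

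**Conclusion.** The concern holds as one about missing support. The stated power reproduces only as an individually randomised comparison against zero, at about 82%, and the documents make no allowance for the site randomisation that they describe. If 90 is the analysis SD, the claim survives a design effect of at most about 1.055 on individual df, and does not survive sites − 2 df at any of the assumed site counts. In addition, 140 per arm gives 79.4% even under independence.

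A reader might infer more, and the documents do not support it:

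- That true power is below 80%. It cannot be determined without the ICC, the sites and the baseline correlation.
- That 80% requires strict independence. A very small ICC also keeps it on individual df (80.4% with 30 sites at ICC 0.005).
- That a restated figure must be lower. The direction depends on the baseline correlation.
- That the SAP made a calculation error. At N = 300 its arithmetic is sound for independent participants.

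The results rest on equal site sizes, all 300 participants contributing, a null of zero and, in step 4, an ICC unchanged by adjustment. The point concerns the power statement only and is not an assessment of the primary model.

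**What to change.** Replace the power sentence in the SAP with one computed for the cluster design, stating:

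- the actual number of sites per arm and the mean site size;
- an ICC range and the design effect 1 + (m − 1) × ICC;
- whether the SD of 90 is before or after baseline adjustment, with the assumed correlation if a gain is claimed;
- that the null is zero, the reading that reproduces the present figure;
- a t reference on site-level degrees of freedom.

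Report the resulting power across the ICC range, or the minimum detectable difference, in place of the present claim.

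The cost is SAP wording and a short recalculation. Enrolment, data and primary model do not change. The downside is that the restated power may be less favourable than the present figure.
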